**A Double-Blind, Randomized, Placebo Controlled, Clinical Trial of an Antiplaque Chewing
Gum (30 mg) – Phase 2 Proof of Concept in a Generally Healthy Patient Population**

Statistical Analysis Plan

Final

28 February 2017

Sponsor The Surgeon General, Department of the Army

Senior Statistician [name]
ClinSmart CRO
[name]
Langhorne, PA 19047
[contact]
[contact]
Email: [contact]

Statistical Analysis Plan

**A Double-Blind, Randomized, Placebo Controlled, Clinical Trial of an Antiplaque Chewing
Gum (30 mg) - Phase 2 Proof of Concept in a Generally Healthy Patient Population**

Signature Page

Prepared by:  Date: 2/28/2017
[name]
ClinSmart CRO
[name]
Langhorne, PA 19047

[name]
[name]
Digitally signed by
[name]
DN: c=US, o=U.S. Government, ou=DoD,
ou=PKI, ou=CONTRACTOR,
cn=[name]
Date: 2017.02.28 11:11:49 -05'00'
Approved by: 8 Date: _____
[name], MBA, MS, PhD (Contractor – TGS)
Biostatistics Support
Clinical Services Support Division
U.S. Army Medical Material Development

1. Synopsis

Name of Sponsor: The Surgeon General, Department of the Army
Name of Investigational Product: Anti-Plaque Chewing Gum (APCG)
Name of Active Ingredient: KSL-W (30 mg)
Title of Study: A Double-Blind, Randomized, Placebo-Controlled, Clinical Trial of an Antiplaque Chewing Gum (30 mg) - Phase 2 Proof of Concept in a Generally Healthy Patient Population
Study Center: Salus Research [name]
Principal Investigator: [name], MPA
Sub-Investigator: [name], RDH, BSEd, MS
Study Period (years): Estimated date first subject enrolled: August 2016 Estimated date last subject completed: August 2016
Objectives: Primary: 
To assess the safety and tolerability of KSL-W (30 mg dose) delivered in a chewing gum formulation compared to a placebo gum formulation Secondary: 
To assess the proof of concept change in plaque regrowth from baseline in the Quigley Hein-Turesky Plaque Index (QHT) of KSL-W (30 mg dose) compared to a placebo gum formulationTo evaluate the proof of concept of KSL-W (30 mg) in change in plaque regrowth based on sub-scores from specific regions of the upper jaw, lower jaw, buccal and lingual surface based on the QHT
Methodology: This study is a Phase 2 two-armed placebo-controlled, double-blind, randomized (1:1), multiple dose, single center study to evaluate the safety and proof of concept of 30 mg KSL-W administered in a chewing gum formulation 3 times per day over 4 treatment days. Oral hygiene (teeth brushing, flossing and/or mouth wash rinse) is prohibited throughout the trial beginning 12 to 16 hours before both the screening and Baseline (Day 0) visits, during the 4 days of treatment (Days 0, 1, 2, and 3) and ending after the periodontal examination and plaque assessment on Day 4. The ability of KSL-W to reduce existing supragingival plaque will be assessed. The oral soft (OST) and oral hard tissues (OHT) will be examined. Changes from baseline, such as soft tissue erythema, ulceration and sloughing, will be noted.
Estimated Number of Subjects Screened: 36
Estimated Number of Subjects Enrolled: 26
Number of Subjects (planned): 24
A sample size of at least 12 subjects per study arm (KSL-W, Placebo) yields at least a posterior 94% chance of observing any KSL-W improvement in the sample mean QHT scores, and at least an 81% posterior chance (given that an improvement was observed) that the projected sample size for a similar, later-phase, confirmatory study, using a 2-tailed $p = 0.05$, power = 90% criterion, is no more than 100 per study arm. This is based on the results of the phase 2a trial at Day 14, where for the 30-mg dose the observed QHT mean change from baseline was -0.31 with $n= 7$ subjects, and for the placebo subjects the QHT mean change from baseline was -0.03 with

n = 16. The observed QHT error standard deviation was 0.22. It was assumed that these Day 14 results from phase 2a apply to this study having 4 days of treatment.

Diagnosis and Main Criteria for Inclusion/Exclusion:

Male and female subjects between the ages of 18 and 64 (inclusive at the time of screening) who are in good health with a minimum of 20 natural teeth will participate in this study.

Investigational Product Dosage, Schedule, and Mode of Administration:

Subjects will receive 30-mg oral doses of KSL-W or placebo chewing gum in tablet form. After a dental examination including teeth polishing, subjects will receive the first dose under supervision in the clinic. The remaining 11 doses will be self-administered and unsupervised. The maximum dose of KSL-W in a 24 hour period is three 30-mg chewing gum tablets (90 mg total). Each dose consists of 1 piece of gum (tablet). The gum will be chewed for 20 minutes balanced equally as possible between both sides of the mouth. The gum will be chewed preferably after a meal or in 4-6 hour intervals three times a day for a total of 4 days.

Duration of Treatment: 4 days

Reference Therapy, Dosage, Schedule, and Mode of Administration:

This is a double-blind, two-armed, randomized placebo-controlled study. The KSL-W and placebo tablets will be identical in appearance.

Criteria for Evaluation:

Safety:

Occurrence of local oral mucosal reactions; systemic reactions such as fever, nausea, headache, diarrhea, and changes in blood pressure; and serious total body reactions will be assessed. In addition, physical examinations and vital signs will be taken before treatment and at the end of the study.

Proof of Concept (Efficacy/Effectiveness):

Changes in the Quigley-Hein TureskyPlaque Index (QHT) will be calculated as whole-mouth scores. Average scores of selected subsets of measurements sites (interproximal, facial, lingual, maxillary, mandibular, and posterior) will be calculated as exploratory endpoints.

Statistical Methods:

Two evaluators will be used for this study, and each subject's randomly assigned evaluator will stay with that subject throughout the study. The randomization to the study arm (KSL-W, placebo) will be 1:1 within evaluator. All adverse events (AE) will be presented in by-subject data listings. Treatment-emergent AEs will be tabulated where treatment-emergent is defined as any AE that occurs after administration of the first dose of study treatment, or any medical or dental condition that is present at baseline but worsens in intensity subsequent to the administration of the first dose of study treatment. In addition to the subject listings, summaries by study arm, noting severity and relationship to study treatment, will include AE incidence proportions and rates by system organ class (SOC) and by preferred term (PT) within SOC. Incidence rates (in events per subject week) will be estimated as the number of treatment emergent AEs divided by the total number of patient-weeks. AE incidence proportion will be estimated based on the number of subjects having at least one AE of a particular type divided by the number of subjects exposed.

Data from physical examinations and vital signs will be summarized for each evaluation time point. Any abnormal physical examination findings noted at the end-of-study exam on Day 4 will be tabulated as a listing. For vital signs, change from baseline to the end-of-study evaluation time points will be summarized.

The primary proof of concept (efficacy) endpoint will use the QHT whole-mouth scores from the full analysis set (FAS) and will be based on the mean change from baseline to Day 4. The QHT whole-mouth average will be the average of scores only from surfaces evaluable for QHT. The QHT score is based on each subject having at least 20 teeth with 6 evaluable surfaces per tooth.

An analysis of covariance (ANCOVA) model will be used to compare 30 mg KSL-W with placebo. The primary model will include the baseline score and study arm (KSL-W, placebo). Sensitivity assessments will be employed to determine whether the effects of treatment on the slope of the baseline covariate, and the effect of evaluator on the treatment placebo comparison can be ignored.

While a formal *p* value comparison based on the final primary ANCOVA model will be generated and summarized, this will not be the primary evaluation, since this study has not been powered for detection of a minimally clinically important improvement in QHT. The primary summaries for this study will include the

estimated difference, KSL-W minus placebo, in the mean (QHT) change from baseline, and the estimated error standard deviation from the primary ANCOVA model. This information will be critical to assessing the chances for a successful demonstration of KSL-W efficacy in future phase 3 studies, as a function of the sample size of these studies.

Similar ANCOVA models will be used for the per protocol (PP) population, and secondary mean scores (FAS and PP), and the results from each model will be summarized.

Descriptive and inferential summaries for FAS and PP will be presented for all scores by study arm overall, and by study arm and evaluator. The summaries will include the mean, standard error, minimum, 25th percentile, median, 75th percentile, and maximum, for baseline, Day 4, and change from baseline to Day 4. *P* values will be given for study arm comparisons but will not be adjusted for multiple comparisons.

Missing data will not be imputed. A missing QHT score will occur if there are insufficient numbers of surfaces evaluable for QHT. A subject will be considered lost to follow-up if their Day 4 morning evaluation occurs more than 24 hours after the scheduled time.

2. Table of Contents

Title Page	1
1. Synopsis.....	3
2. Table of Contents	6
3. List of Abbreviations and Definitions of Terms.....	8
4. Study Objectives.....	10
4.1. Primary Objective.....	10
4.2. Secondary Objectives	10
5. Study Design	10
5.1. Randomization.....	12
5.2. Blinding	13
5.3. Procedures for Unblinding	14
5.4. Sample Size Justification.....	15
6. Statistical Procedures.....	15
6.1. Data Handling Conventions	15
6.1.1. Study Analysis Populations.....	15
6.1.2. Study Exposure.....	15
6.2. Specification of Safety Measurements (Endpoints)	16
6.2.1. Vital Signs	16
6.2.2. Physical Examination	16
6.2.3. Intraoral Examination.....	16
6.2.4. Adverse Event Determination and Assessment.....	17
6.3. Proof of Concept Evaluations (Secondary Analysis)	21
6.3.1. Quigley Hein-Turesky Plaque Index (QHT) Whole Mouth Score.....	21
7. Statistical Methods for Data Analysis	22
7.1. Primary (Safety) Analyses.....	22
7.1.1. Adverse Events.....	22
7.1.2. Vital Signs	23

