12.1.2.1 Proof of Concept Analyses (Secondary)

The QHT whole mouth average, determined at baseline and Day 4, will be the average of scores from surfaces evaluable for QHT. In order to qualify for this study each subject must have at least 20 teeth with 6 evaluable surfaces per tooth.

An analysis of covariance (ANCOVA) model will be applied to each subject's change in plaque regrowth from baseline in the QHT score (baseline minus Day 4) for subjects in the primary analysis population (FAS defined in [section 12.8](#) below). The primary model will include study arm (KSL-W, placebo) and the baseline QHT score.

Estimates and 95% confidence bounds on all model parameters will be summarized, and the estimated mean study arm difference from the final ANCOVA model will be presented along with its standard error and 95% confidence bound. A 2-tailed p-value for this difference will also be presented as a further descriptive summary.

The estimated mean difference together with the error standard deviation from the primary ANCOVA model will be used to forecast success of future studies based on the average power for detecting a KSL-W improvement in the QHT reduction as a function of the future study sample size.

Secondary analyses involving the change in plaque regrowth will include a full model with the baseline QHT score, study arm, evaluator and all interactions of these terms. This model will be used to assess the overall effect of evaluator on the results, and any study arm difference in the slope terms of the baseline QHT score.

In addition to the model interaction evaluations described above, the assumption of equal error variance across the design will be checked using scatter plots and the estimated study arm standard deviations. The linearity assumption of mean reduction in QHT versus baseline QHT will be checked using scatter plots.

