12.2 Planned Enrollment and Reason for Sample Size

A sample size of at least 12 subjects per study arm (KSL-W, Placebo) yields at least a posterior 94% chance of observing any KSL-W improvement in the sample mean QHT scores, and at least an 81% posterior chance (given that an improvement was observed) that the projected sample size for a similar, later phase, confirmatory study, using a 2-tailed $p = 0.05$, power = 90% criterion, is no more than 100 per study arm. This is based on the results of the phase 2a trial at Day 14, where for the 30 mg dose the observed QHT mean change from baseline was -0.31 with $n = 7$ subjects, and for the placebo subjects the QHT mean change from baseline was -0.03 with $n = 16$. The observed QHT error standard deviation was 0.22. It was assumed that these Day 14 results from the phase 2a study will apply to this study having 4 treatment days.

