12.3 Level of Significance to be Used

While formal p-value comparisons of the study arms based on the ANCOVA model results will be generated and summarized (2 tailed, $p = 0.05$), these will be considered only as descriptive summaries since this study has not been powered for detection of a minimally clinically important improvement in QHT. The primary summaries for this study will include the estimated difference, KSL-W minus placebo, in the mean (QHT) reduction from baseline, and the estimated error standard deviation from the final ANCOVA model. This information will be critical to assess the chances for a successful demonstration of KSL-W efficacy from future phase 3 studies, utilizing QHT as a function of the sample size of these studies.

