5.4. Sample Size Justification

A sample size of at least 12 subjects per study arm (KSL-W, Placebo) is planned. This projection was based on certain results from the phase 2a trial (sponsor study number S-11-14). At Day 14, for the 30 mg dose ($n = 7$ subjects) the observed QHT mean change from baseline was 0.31 and for placebo ($n = 16$ subjects) the observed QHT mean change from baseline was 0.03. The observed QHT error standard deviation was 0.22. Using these results to form the basis of a prior joint distribution of means and error variance, a sample size of at least 12 subjects per study arm (KSL-W, Placebo) yields at least a posterior 94% chance of observing any KSL-W improvement in the sample mean QHT scores, and at least an 81% posterior chance (given that an improvement was observed) that the projected sample size for a similar, later phase, confirmatory study, using a 2-tailed $p = 0.05$, power = 90% criterion, is no more than 100 per study arm. It was assumed that these Day 14 results from phase 2a apply to this study having 4 days of treatment.

6. Statistical Procedures

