7.2. Plaque Re-growth: Secondary Proof of Concept Analyses

7.2.1. Whole Mouth QHT Score

An analysis of covariance (ANCOVA) model will be fit to the subjects’ change in plaque re-growth from baseline in the QHT score (baseline minus Day 4) for subjects in the FAS population.

Primary POC model: The primary model will include randomized study arm (KSL-W, placebo) and the baseline QHT score.

Least squares means and standard errors will be summarized for KSL-W, placebo, and the KSL-W minus placebo mean difference. A 95% confidence bound will be presented for the mean difference along with a 2-tailed p value testing the null hypothesis that the mean difference in the mean change in plaque re-growth is zero. The estimated common error variance together with a 95% (equal tailed) confidence bound will be presented.

The model assumptions include the following:

- Baseline minus Day 4 subject QHT differences have a normal distribution, conditioned on the baseline observation.

- The relationship between the mean difference and baseline is linear, with slope not dependent on study arm.
- The model error variance does not depend on study arm or the mean difference.
- The QHT evaluator has no effect on the mean difference, error variance, or baseline slope.

Each of these model assumptions will be checked, and the findings of these determinations will be summarized along with the above information. Violations of the model assumptions affecting later decisions based on this information will be investigated, particularly their impact on the conclusions of the study.

Secondary Investigations: A secondary investigation involving a full model including study arm, baseline QHT score, QHT evaluator and all possible 2-factor interactions will be conducted.

Results of the primary model applied to the per-protocol (PP) population whole-mouth QHT scores will be summarized as with the FAS population, as well as the primary and secondary model parameter estimates for the PP population.

This study was not powered for a specific expected effect size, hence all p values are descriptive and no adjustment will be made for multiple p values.

The results of the primary and secondary investigations will be summarized in a Statistical Analysis Report (SAR), including the model assumptions investigations and estimates, standard errors of the primary and secondary model parameters.

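### The primary ANCOVA should include evaluator: 24 subjects cannot show that its effect on the arm comparison is ignorable

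*SAP*

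**What the plan says.** **Primary model.** Protocol 12.1.2.1 and SAP 7.2.1 both fix the primary ANCOVA as study arm plus baseline QHT score. Evaluator is not in it.

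**Checks.** Both synopses plan sensitivity assessments to establish whether treatment affects the baseline slope and whether "the effect of evaluator on the treatment placebo comparison can be ignored". SAP 7.2.1 lists as a model assumption: "The QHT evaluator has no effect on the mean difference, error variance, or baseline slope". It promises to check each assumption and to investigate violations. Neither document gives a test, significance level, margin or consequence for these checks.

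**Secondary model.** SAP 7.2.1 adds a full model with arm, baseline, evaluator and their two-factor interactions. Its estimates and standard errors are to be reported, and all p values are descriptive.

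**Which model supplies the results.** Protocol 12.1.2.1 presents "the estimated mean study arm difference from the final ANCOVA model", and Protocol 12.3 names as a primary summary the arm difference "and the estimated error standard deviation from the final ANCOVA model". The next paragraph of 12.1.2.1 and both synopses tie the figures used for future studies to the primary model. The synopses take the p value from a model called both final and primary. *Final* is never defined.

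**Allocation.** The SAP synopsis says the arms are randomised 1:1 within evaluator. SAP 5.1 describes one list, with each subject seen by the next available evaluator and given the next number on that list. The two descriptions do not agree.

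**The concern.** If the SAP synopsis is right about allocation, evaluator is a factor used in the randomisation and would normally be in the model. If SAP 5.1 is right, nothing balances evaluators across arms, and the model is the only protection against a chance imbalance. Either way there is reason to include it, and the plan instead asks a small data set to show that it does not matter.

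The arm difference and the error SD are the declared proof-of-concept outputs, intended for judging the prospects and size of later studies. Evaluator variation left in the residual goes straight into that SD. The undefined *final* model adds a second uncertainty: a reader cannot be sure that the reported figures come from the prespecified model rather than from one settled on after the checks.

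**Working it through.** **Inputs from the documents**
- Size: "A sample size of at least 12 subjects per study arm (KSL-W, Placebo) is planned" (SAP 5.4), so 24 subjects.
- Planning difference: phase 2a changes of -0.31 and -0.03 (Protocol 12.2), so 0.31 - 0.03 = 0.28.
- "The observed QHT error standard deviation was 0.22" (SAP 5.4).
- Two evaluators (Protocol 7.3.1).

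**Assumptions**
- Evaluators used equally, so 24/4 = 6 per arm-by-evaluator cell.
- Two-sided alpha 0.05. The Protocol states this level for the arm comparison only.
- Evaluator effects of 0.14 and 0.28 are illustrative; the documents give none. Here an evaluator effect means a difference between evaluators in baseline-adjusted change.

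**The plan's own figures.** The plan states no precision or power for the evaluator check, so there is nothing to reproduce on this point. Its sample-size statement (at least 94% and at least 81%) came out at 97.5% and 91.7% with a vague prior. The SAP does not specify its prior, the results are compatible with its *at least* wording, and nothing below depends on them.

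**1. Arm-by-evaluator interaction**
- SE = 0.22 × √(4/6) = 0.180.
- The full model has 7 parameters (intercept, three main terms, three two-factor interactions), so residual df = 24 - 7 = 17 and t = 2.110.
- 95% half-width = 2.110 × 0.180 = 0.38, against a planning difference of 0.28.
- An interaction of 0.28 means, for example, an arm difference of 0.14 with one evaluator and 0.42 with the other. Power to detect it is 31% (noncentral t, 17 df) or 34% (normal approximation). 80% power needs an interaction of 0.53.

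| Variation | Half-width | Power at 0.28 |
|---|---|---|
| 6 per cell, SD 0.22 | 0.38 | 31% |
| All 26 enrolled, 6.5 per cell | 0.36 | 34% |
| Cells of 4 and 8 in each arm | 0.40 | 28% |
| Cells of 3 and 9 in each arm | 0.44 | 25% |
| SD 0.15 | 2.110 × 0.15 × √(4/6) = 0.26 | 58% |
| SD 0.30 | 2.110 × 0.30 × √(4/6) = 0.52 | 19% |

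**2. Evaluator main effect**
- SE = 0.22 × √(2/12) = 0.090.
- Power is 31% for an effect of 0.14 and 84% for 0.28 (t, 17 df).

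**3. Leaving a main effect e out of the model**
- In simulation the mean arm difference stayed at 0.28, so there is no bias on average.
- With evaluators used equally, error SD ≈ √(0.22² + (e/2)²). For e = 0.14: √(0.0484 + 0.0049) = 0.23. For e = 0.28: √(0.0484 + 0.0196) = 0.26. The simulation agrees.
- Confirmatory N per arm at 90% power, two-sided 0.05: 2 × SD² × (1.960 + 1.282)² / 0.28². SD 0.22 gives 13, SD 0.23 gives 15, SD 0.26 gives 19.

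**4. Chance imbalance if one unstratified list was used**
- Suppose each evaluator sees 12 subjects and arms fall at random. The chance of an 8/4 versus 4/8 split, or worse, is 2 × (495² + 220² + 66² + 12² + 1) / 2,704,156 = 22%. The block size is withheld, and blocking may lower this.
- An 8/4 versus 4/8 split shifts the unadjusted difference by e × (8/12 - 4/12) = e/3, which is 0.05 for e = 0.14 and 0.09 for e = 0.28.

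**5. Cost of including evaluator**
- Residual df goes from 21 to 20, and critical t from 2.080 to 2.086.

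**The case against.** The case for leaving the model alone is substantial.

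- **Design safeguards.** Each subject keeps one evaluator, so a constant scoring offset cancels from the change score, although baseline adjustment can bring part of it back. Protocol 7.3.4 requires calibration beforehand, with a report that evaluator differences are negligible. This makes a large effect less likely but does not adjust for one.
- **Transparency.** The evaluator model is run whatever the checks show. By-evaluator summaries are planned, and shell TREF20.2 gives the arm difference with 95% bounds for each evaluator. This stands, and much of the reporting asked for here is already in the plan. None of it changes the primary difference or SD.
- **Size of harm.** An SD of 0.23 instead of 0.22 is small beside sampling error: a 95% interval for an SD of 0.22 on 21 df runs from about 0.17 to 0.31. Even 19 per arm is far below the planning threshold of 100. This stands too.
- **Fit of the remedy.** An evaluator main effect does nothing about an interaction. That is correct, and is why the fix has separate parts.

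A reader might go further and infer that the plan drops evaluator by a low-powered significance test, so that a real evaluator effect would usually be dismissed. The documents do not support that. They state no test or drop rule, SAP 7.2.1 makes p values descriptive, and the primary model is fixed in advance. The 31% belongs to an interaction of 0.28 (or a main effect of 0.14); a main effect of 0.28 would be detected about 84% of the time. No comparable figure can be given for the slope check, because no baseline SD is stated.

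**Conclusion.** The point holds as a modest but worthwhile correction. At the planning SD, 24 subjects cannot establish that evaluator has no effect on the arm comparison: the interaction is known only to about ±0.38, against an expected difference of 0.28. That half-width does not depend on any test being used. It does assume SD 0.22 and equal use of evaluators. Unequal use makes it wider; an SD as low as 0.15 would bring it to 0.26, just under the planning difference.

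Omitting a real evaluator main effect leaves the difference unbiased on average but inflates the error SD to about 0.23 or 0.26 for the illustrative effects, or 15 or 19 per arm instead of 13 in a later trial. It also leaves the difference exposed to evaluator imbalance if the single list in SAP 5.1 is what was followed.

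*Final* is undefined beside a fixed primary model. That is an ambiguity about the source of the key figures. It does not show that a data-driven choice of model is intended.

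**What to change.** 1. Add evaluator as a prespecified fixed main effect in the primary ANCOVA (both synopses, Protocol 12.1.2.1, SAP 7.2.1), whatever the checks show. Cost: one model term and 1 df.
2. Report the arm-by-evaluator and arm-by-baseline interactions as estimates with 95% confidence intervals from the secondary model already planned, and remove the wording in both synopses about whether these effects are ignorable. Bring TREF20.2 into line: its footnote lists no interaction, yet the shell shows a separate arm difference for each evaluator.
3. Replace *final* with *primary* in Protocol 12.1.2.1 and 12.3, and delete it where both synopses use the two words together.
4. State which allocation was used, within evaluator or one common list, and make the SAP synopsis and SAP 5.1 agree.

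Items 2 to 4 are wording and one table footnote. No new data or subjects are needed.
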